Appendix 1: Criteria and Assumption for Determining Sample Size

Appendix 2: Acute Myocardial Infarction Criteria

Appendix 3. Half-Lives of Some Commonly Used Agents

Appendix 4A & 4B: Age - MI Eligibility Log

Appendix 5: Specific Drugs Considered

1. INTRODUCTION

Although overall mortality from cardiovascular disease has been decreasing for over ten years,¹ sudden cardiac death remains a health problem of epidemic proportions in the United States. Over 400,000 persons die suddenly each year in this country.² It is generally recognized that the majority of patients who experience sudden death have ventricular fibrillation as the precipitating arrhythmia.³ While some fatal arrhythmias may start as organized ventricular tachycardia, these arrhythmias commonly degenerate quickly to ventricular fibrillation.⁴ Only uncommonly is any form of bradycardia responsible for sudden death. The majority of patients who experience sudden death have significant coronary artery disease, often associated with prior myocardial infarction, angina pectoris, hypertension, and impaired ventricular function.⁵ Therefore, if patients could be identified and if adequate therapy were available, reduction in sudden death could be attained.

Certain patient groups have been identified as having a high risk of sudden cardiac death:

- a. survivors of recent myocardial infarction;⁶⁻⁸
- b. resuscitated survivors of ventricular fibrillation not associated with an acute transmural myocardial infarction;⁹⁻¹¹
- c. patients with recurrent ventricular tachycardia.¹²⁻¹³

The numbers of patients with recurrent ventricular tachycardia or survivors of ventricular fibrillation not associated with a myocardial infarction are difficult to assess. Nevertheless, the largest of these high risk populations in the United States is the post myocardial infarction group. There are approximately 350,000 patients discharged from the hospital with a myocardial infarction as the primary diagnosis each year in this country. The cumulative risk for cardiac death in the year after myocardial infarction is from 8 to 15%. However, certain characteristics have been identified in the last 15 to 20 years which allow stratification of patients into high risk subsets. Many factors place patients at high risk, although these factors are commonly interrelated: advanced age, male sex, previous myocardial infarction, congestive heart failure, persistent sinus tachycardia, ventricular arrhythmias beyond the acute phase of the infarction, etc. Early studies have suggested that the major factor in determining the risk of death in the year after myocardial infarction is left ventricular function,¹⁴ but it has become apparent that ventricular arrhythmias constitute an independent predictor of death.^{6,15,16} Since frequent and complex ventricular arrhythmias are associated with sudden death, one might hypothesize that therapy that suppressed these arrhythmias would improve survival. If this hypothesis is true, either the suppressed arrhythmias are etiologically related to the sudden death, or, alternatively, successful therapy alters both the factor responsible for sudden death and the markers of risk, the ventricular premature depolarizations (VPD's).

Recent placebo-controlled secondary intervention trials in the post myocardial infarction population have shown an improved survival for patients treated with beta blockers.¹⁷⁻²⁵ A significant reduction in overall cardiac death, and in some a reduction in sudden death, has been demonstrated for many of the beta blockers (timolol, propranolol, practolol, and metoprolol). It still is

uncertain whether the mechanism of this improved survival was reduction of ischemia, prevention of reinfarction, suppression of arrhythmias, or a combination of these or other factors.

In spite of attempts to show that suppression of VPD's after a myocardial infarction might be beneficial, no study to date has been designed or executed properly to achieve this goal. Furberg²⁶ summarized the studies in post infarction patients and emphasized that methodologic discrepancies in each study could account for the failure to show a benefit from antiarrhythmic therapy: (1) failure to select patients at high risk with arrhythmias post MI; (2) too few patients studied to expect to observe a difference between treated and untreated patients (i.e., the power of the study was too small); (3) the agents chosen were ineffective or given in the wrong dose (e.g., in some studies, dose titration was not performed); (4) only a single drug was tested without the option to proceed to a second drug if the first was ineffective in controlling arrhythmias; or (5) too many patients dropped out of the study due to adverse side effects of the drugs. Thus, studies with phenytoin,²⁷⁻²⁸ aprindine,²⁹ mexiletine³⁰⁻³¹ and tocainide³²⁻³³ all were inadequate to show an improvement from drug therapy. However, with the current ability to identify patients with arrhythmias after myocardial infarction, it should be possible to design a study with antiarrhythmic agents which would be able to show the reduction of post infarction arrhythmic death, if such a beneficial effect of the drugs exist.

Arrhythmias in the post myocardial infarction setting have usually been detected by 24 hour Holter recording. Even short term one hour recording has identified ventricular arrhythmias as an independent risk factor in the post myocardial infarction patient. Ruberman¹⁶ concluded that complex VPD's on a one hour in-office monitor identified the patient at risk for total cardiac and sudden cardiac death. Bigger³⁴ and Moss³⁵ likewise found that frequency and complexity of VPD's correlated well with sudden cardiac death after myocardial infarction. The ideal antiarrhythmic drug trial would include only those patients at high risk of arrhythmic death, and patients would be treated with a drug which was easy to administer with few adverse effects. The Cardiac Arrhythmia Pilot Study (CAPS) was begun in 1982 in an attempt to determine whether adequate numbers of patients could be identified and randomized after myocardial infarction to make a large-scale study feasible.³⁶

In the United States, as of December 1982, only quinidine,³⁷⁻³⁸ procainamide,³⁹ and disopyramide,⁴⁰ had been approved for chronic use to treat ventricular arrhythmias. These drugs, however, had insufficient antiarrhythmic potential, and all were relatively poorly tolerated. New drugs were then being tested which could have efficacy in suppressing arrhythmias with fewer major adverse effects. The toxic - therapeutic ratio of these drugs (e.g., encainide, flecainide, moricizine, imipramine, amiodarone, lorcainide, mexiletine, aprindine, sotalol, and propafenone) potentially could have been better than marketed antiarrhythmic drugs in the United States in 1982. Although all drugs can have proarrhythmic effects and other adverse effects, some of these drugs seemed to have a substantial efficacy in suppressing both VPD's and more complex arrhythmias with few reported adverse effects. With the increased clinical investigational use of these drugs, it was desirable to determine their ability to suppress arrhythmias in this post myocardial infarction population and to assess their safety and tolerance in CAPS, which was planned as the pilot study for a later, large-scale trial with mortality as an end

point. Preliminary calculations suggested that to conduct such an adequate large-scale trial with mortality due to arrhythmia as the endpoint, it would be necessary for an antiarrhythmic treatment to reduce VPD rates by approximately 70% compared to baseline in at least 80% of patients. Because it was not known whether any of the newer antiarrhythmic drugs were capable of this suppression rate without intolerable adverse effects, CAPS was conducted.

CAPS had three main goals: 1) to demonstrate that patients could be identified and recruited who would be willing to comply with the study protocol; 2) to determine whether a treatment regimen was available which would initially provide 70% or greater VPD reduction in at least 80% of the patients and maintain substantial reduction for one year without intolerable adverse effects; and 3) to study the one year course of arrhythmia in placebo-treated patients.

CAPS was a double-blind, randomized trial which evaluated the long-term (one year) antiarrhythmic effects of encainide, flecainide, imipramine, and moricizine, compared with placebo. Ten clinical centers, a coordinating center, a drug distribution center, a Holter reading center and the National Heart, Lung, and Blood Institute (NHLBI) project office participated in this study. Details of the protocol, including rationale for drug selection, are given elsewhere.^{36,41-42} In brief, patients were eligible if they had suffered an MI between 6 and 60 days earlier, were less than 75 years of age, had a left ventricular ejection fraction $>.20$, had no contraindications to any of the medications, provided informed consent, and demonstrated an average of at least 10 VPD's per hour or at least 5 episodes of unsustained ventricular tachycardia (VT) on a 24 hour Holter. The presence of consecutive VPD's (runs) of 10 or more at a rate ≥ 100 per minute was an exclusion criterion because of the concern that patients with such an arrhythmia had a substantial risk of sudden death, could not be treated in a protocol which included a placebo, and would ultimately be given individualized treatment.

After qualifying and giving informed consent, patients were randomly assigned to one of four active drugs or to a placebo. If efficacy, defined as at least 70% reduction of VPD's and more than 90% reduction of runs (3 to 9 consecutive VPD's), was not achieved with dose titration on the first drug, or if there were proarrhythmia, disqualifying VT, conduction abnormalities (including heart block and excessive lengthening of the QRS or QT) or intolerable adverse effects, dose titration with a second agent (which was part of the original randomization assignment) was begun. Placebo patients who demonstrated lack of efficacy were switched to a second placebo. The active drugs and the three dose levels chosen for each are shown below:

Total Daily Dose

Drug	Low Dose	Medium Dose	High Dose
Encainide	105mg	150mg	180mg
Flecainide	200mg	300mg	400mg
Imipramine	150mg	225mg	375mg
Moricizine	600mg	750mg	900mg

The study was conducted in 502 post myocardial infarction patients who were followed for one year after randomization.

CAPS determined that it was feasible to enroll and follow sufficient patients and to maintain high levels of patient compliance to the study protocol. CAPS also showed that at least two drugs, encainide and flecainide, reduce ventricular ectopy by $\geq 70\%$ (79% and 83% of patients, respectively) and maintain an average reduction of $\geq 70\%$ in many (75% and 73% of patients, respectively) for at least one year. Of the other active drugs, the initial suppression rates were 52% on imipramine, 66% on moricizine and 37% on placebo.

It would appear that encainide and flecainide were both adequate therapies to achieve the goal of 70% suppression of VPD's in 80% of patients. The initial success rates for encainide and flecainide as first drug were virtually identical, with approximately 80% of patients with greater than 70% average reduction of VPD's on these drugs, compared to 37% with placebo. Long-term tolerance of both drugs met the goals of the study, 78% of patients who were assigned encainide at completion of titration remaining on the drug throughout the year, and 75% of patients assigned flecainide remaining on the drug for the year.

A surprising number of patients (25%) developed new or worsened congestive heart failure (CHF). There may have been some differences between encainide and flecainide in their negative inotropic effects. More patients developed new or worsened congestive heart failure on flecainide than on encainide, a difference which is probably real, even considering the difficulties encountered in this study with the rather subjective definitions of new or worsened congestive heart failure. However, it must be noted that the incidence of new or worsened congestive heart failure on placebo fell between that for flecainide and encainide and that only 26 of 502 patients had to stop the CAPS medication because of new or worsened CHF.

Twelve percent of all patients in CAPS developed disqualifying ventricular tachycardia (defined by the investigators as a run of 10 or more ventricular complexes at a rate of ≥ 100 per minute), and which, by protocol, required cessation of the study drug. However, most of the disqualifying runs were unsustained and asymptomatic with length < 15 beats. In addition, of all patients assigned CAPS therapy (active or placebo) at completion of titration, 19% were changed to individualized therapy by the end of the first year. Fifteen percent of the patients assigned at end of titration to encainide and 18% of those assigned to flecainide went on individualized therapy. The impact of these findings on the subsequent large scale study must be considered.

One of the major concerns in CAPS was the potential for adverse reactions and proarrhythmic effects of drugs. Hospitalization was therefore required for initiation or change in drug therapy. CAPS demonstrated that the immediate adverse effects and proarrhythmic effects of these drugs were relatively small and equivalent to placebo, remembering that the study excluded patients with ejection fractions ≤ 0.20 , included slow titration of doses and excluded patients with ≥ 10 beats in a row of ventricular tachycardia on the baseline Holter recording.

The Cardiac Arrhythmia Pilot Study thus suggested that the large scale study, the Cardiac Arrhythmia Suppression Trial (CAST), can be successfully completed. Patients with sufficient ectopy to qualify as moderately high risk can be identified after a myocardial infarction and enrolled in such a study. CAPS showed, however, that many patients must be screened to enable enrollment of sufficient numbers of patients to test the hypothesis that VPD suppression improves survival. With at least two drugs in CAPS (encainide and flecainide), VPD's were successfully suppressed with adequate patient compliance and acceptable adverse effects. Thus, it will be feasible to test whether suppression of VPD's will improve survival in patients who have arrhythmias after a myocardial infarction.

2. OVERVIEW OF STUDY DESIGN

In this section we give a brief simplified description of the CAST design. The details are given in subsequent sections.

A. Objective.

The Cardiac Arrhythmia Suppression Trial (CAST) is designed to determine whether drug therapy results in a reduction in arrhythmic death (as defined below) for patients in whom drug therapy does suppress ventricular arrhythmia. Patients will be randomized during an open label titration phase to a sequence of two or three antiarrhythmic therapies depending upon cardiac ejection fraction. Patients whose arrhythmia is adequately suppressed will then be randomized to the therapy which suppressed the arrhythmia or to a matching placebo. Patients without adequate suppression of arrhythmia will be randomized to the best therapy or to a matching placebo. They will constitute a major substudy, not a subgroup of the main study.

B. Patient Eligibility.

The study participants will be survivors of a myocardial infarction who have 6 or more VPD's/hr on a 24 hour Holter obtained between 6 days and 2 years after the onset of the myocardial infarction. If the screening Holter is obtained between 6 and 90 days after the onset, the patient's ejection fraction must be ≤ 0.55 , whereas if the screening Holter is obtained 90 or more days after the onset of myocardial infarction, the ejection fraction must be ≤ 0.40 . In the latter case, if the ejection fraction is ≥ 0.30 it must have been obtained within 90 days prior to the qualifying Holter.

Patients with a run of VT of ≥ 15 complexes at a rate ≥ 120 per minute or patients with symptomatic hemodynamically important ventricular tachycardia will be excluded from the study because of the likelihood that the private physician would prefer to treat them with an antiarrhythmic drug.

C. Treatment

During the titration phase, three active drugs will be used (at least initially). These drugs (encainide, flecainide, and moricizine) will be used in a number of sequences which will be assigned randomly. The sequence will contain three drugs for patients with an ejection fraction ≥ 0.30 and two drugs, encainide and moricizine, for patients with an ejection fraction < 0.30 . Each drug has two dose levels, and dosing will proceed from the low to the high dose for each drug. Suppression or lack thereof will be documented by a 24 hour Holter. (However, a Holter will not be necessary if limiting adverse effects are present.)

Following the titration phase, patients whose arrhythmia was successfully suppressed will be randomized to the successful therapy or to a matching placebo. Patients whose arrhythmia was not successfully suppressed (though not included in the primary analyses) will be randomized to the best

therapy, that which is most effective among those which are tolerated and which do not increase the VPD rate, or to a matching placebo. During titration, suppression will be defined as $\geq 80\%$ reduction in the VPD rate and $\geq 90\%$ suppression of runs of VT (3-14 VPD's at a rate ≥ 120 per minute).

D. Endpoints

The primary endpoint in the suppression trial will be arrhythmic death as defined below.

Arrhythmic death is defined as (1) death occurring in less than 24 hours from the onset of new symptoms in the absence of severe left ventricular failure or shock which in itself might have been expected to cause death; (2) resuscitated ventricular fibrillation (or, if no rhythm documentation is available, resuscitated cardiac arrest; i.e., resuscitated ventricular tachycardia is not to be counted as an "arrhythmic death"); (3) unwitnessed death without other known noncardiac causes.

In the absence of documentation to the contrary, death occurring in < 24 hours from onset of symptoms will be considered to be a sudden arrhythmic death as long as the only new symptoms were ischemic pain or pressure, syncope, palpitations or dizziness, and as long as the patient died of documented or presumed arrhythmia. Death which occurs as the end result of CHF/shock, even though occurring in < 1 hour from onset of symptoms, will not be considered to be sudden arrhythmic death. In circumstances where the event is witnessed but poorly documented, or for other cardiac conditions, death or cardiac arrest which occurs within 1 hour of onset of symptoms will be considered to be arrhythmic. If any symptoms are separated from onset of death/cardiac arrest by a symptom-free period of 24 hours, then these symptoms will not be considered as part of the death/cardiac arrest event itself.

Secondary endpoints will include:

- (1) total cardiac mortality
- (2) the combination of sustained ventricular tachycardia and arrhythmic death
- (3) total overall mortality (both cardiac and non-cardiac)

Additional objectives of the study will be to evaluate:

- (1) the relationship of baseline ejection fraction to the primary and secondary endpoints
- (2) the relationship of the time at which drug therapy is initiated to the primary and secondary endpoints
- (3) the relationship of other baseline characteristics to the primary and secondary endpoints
- (4) suppressable versus unsuppressable patients
- (5) the effect of antiarrhythmic therapy on congestive heart failure

Primary analyses will be by intention to treat and will be one-sided, with an alpha value of 0.025. Safety (adverse effects, including potential proarrhythmia) will be monitored by the Data and Safety Monitoring Board.

E. Duration and Estimated Sample Size

Patients will be enrolled for three years, and all patients will be followed to a common termination date, which will be two years beyond enrollment of the last patient. It is expected that 4400 patients will be enrolled into the main study during this period. This number will provide a power of at least 85% to detect a 30% reduction in arrhythmic death. It is expected that 800 to 1200 patients will be enrolled into the substudy of patients with inadequate suppression of VPD's. Because the incidence of arrhythmic death in these patients is unknown, power calculations are problematical. Details of the sample size calculations are included in Appendix 1.

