Appendix 1: Criteria and Assumption for Determining Sample Size

Estimation of Sample Size for CAST

In order to estimate the sample size for CAST, the following assumptions have been made:

1. All participants will be followed for a minimum of three years.
2. The primary endpoint, sudden cardiac mortality, is projected to have a three year incidence of 11% in the placebo group.
3. The use of antiarrhythmic therapy is expected to reduce the incidence of sudden cardiac death by 30%.
4. The Type I or α error was set at a one-tail level of 0.025. The power of the study to detect the hypothesized difference of 0.84.
5. It was assumed that 6% of the placebo group would be assigned antiarrhythmic therapy by their private cardiologists during the study (2% per year).
6. It was also projected that 30% of the patients in the intervention group would stop taking the assigned medication (20% in year one, and 5% in each of the next two years).

These assumptions resulted in the need to randomize 2200 patients to each of the groups - placebo and treatment.

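### Section 2.E claims at least 85% power with a two-year minimum follow-up, but Appendix 1, which it cites, gives 0.84 on a three-year minimum

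*Protocol*

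**What the plan says.** Section 2.E (Duration and Estimated Sample Size) plans an enrolment period of three years. On the end of follow-up it says: "all patients will be followed to a common termination date, which will be two years beyond enrollment of the last patient". It expects 4400 patients in the main study and adds: "This number will provide a power of at least 85% to detect a 30% reduction in arrhythmic death". For details it sends the reader to Appendix 1.

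Appendix 1 lists its assumptions. On follow-up: "All participants will be followed for a minimum of three years". On power: "The power of the study to detect the hypothesized difference of 0.84". It arrives at 2200 patients per group, which is the same 4400.

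The test level agrees. Section 2.D has "Primary analyses will be by intention to treat and will be one-sided, with an alpha value of 0.025", and Appendix 1 has "The Type I or α error was set at a one-tail level of 0.025".

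The 1989 revision, items 7 and 11, extends recruitment and follow-up and restates power as about .73 for 1675 patients. It does not touch section 2.E or Appendix 1, and it says that nothing beyond its listed changes was approved.

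**The concern.** Sample size, effect and level are the same in both places, so the two power figures should match. A calculation that yields 0.84 cannot be the source for a floor of 85%, and rounding does not close the gap. The follow-up conditions also differ: a patient enrolled in the last year of accrual has between two and three years before the common termination date, so the appendix's three-year minimum fails for that patient. A reader cannot tell which follow-up the stated power assumes, or whether the design as scheduled has that power. The base protocol remains the record of the original design, so the discrepancy stays on file.

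**Working it through.** **Inputs.** From Appendix 1: placebo incidence 11% at three years; 30% reduction (to 7.7%); one-sided level 0.025; 2200 per group; drop-out from active therapy 20%, 5% and 5% in years 1 to 3; drop-in on placebo 2% a year. From section 2.E: three years of enrolment, with the last patient followed for two years. Appendix 1 calls its endpoint sudden cardiac mortality; I take this as section 2's arrhythmic death.

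**Not stated, so assumed and varied.** When within a year crossover happens; crossover after year 3; the shape of the hazard; whether the 30% is a cut in three-year incidence or a hazard ratio of 0.70. Accrual is taken as uniform, which gives 2 to 5 years of follow-up, mean 3.5.

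**Formulas.** Constant placebo hazard: −ln(0.89)/3 = 0.0388 per year. As a cut in incidence, the 30% means a hazard ratio of ln(0.923)/ln(0.89) = 0.688. Patients off active therapy take the placebo hazard; placebo patients who drop in take the treated hazard. Group incidences pC and pT are averaged over follow-up, and

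power = Φ{[(pC − pT) − 1.96·√(2p̄(1 − p̄)/n)] / √[(pC(1 − pC) + pT(1 − pT))/n]}, with n = 2200 and p̄ the mean of pC and pT.

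**Bounds at a fixed three years.** No crossover (11% against 7.7%): 0.964. Full 30% and 6% crossover from day 1 (10.80% against 8.69%): 0.656.

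**The plan's 0.84.** A fixed three-year comparison, hazard ratio 0.70, crossover at the end of each year: 10.94% against 8.32%, power 0.839. This reproduces the appendix's figure, but it is not the only route to it.

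**Section 2.E design, follow-up 2 to 5 years, constant hazard.** In each cell the first figure stops crossover after year 3; the second continues it at 5% and 2% a year.

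| Crossover within each year | 30% as cut in incidence | Hazard ratio 0.70 |
|---|---|---|
| At the start | 0.788 / 0.768 | 0.752 / 0.732 |
| Spread evenly | 0.843 / 0.835 | 0.811 / 0.802 |
| At the end | 0.888 / 0.885 | 0.860 / 0.857 |

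Example (evenly spread, cut in incidence, first figure): pC = 0.1254, pT = 0.0972, p̄ = 0.1113. The numerator is 0.0282 − 1.96 × 0.00948 = 0.0096 and the denominator is 0.00947, so z is about 1.01 and power about 0.84.

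**Other follow-up windows, evenly spread crossover.** Fixed three years: 0.813 (cut in incidence) or 0.778 (hazard ratio 0.70). A true three-year minimum with three years of accrual, that is 3 to 6 years: 0.898 / 0.878 or 0.871 / 0.849. The change from 3–6 to 2–5 years costs 4 to 6 points (0.898 − 0.843, 0.878 − 0.835, 0.871 − 0.811, 0.849 − 0.802).

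**Front-loaded hazard (assumed), 2 to 5 years.** With more of the 11% falling in year 1, for example 6%, 3% and 2% over the first three years and 2% a year after, evenly spread crossover gives about 0.86 on the incidence reading and about 0.83 with hazard ratio 0.70. End-of-year crossover on the incidence reading gives 11.94% against 8.87%, power 0.916.

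**The case against.** The strongest reply is that the verifiable gap in power is one percentage point, in a section that presents itself as a simplified overview, and that revision items 7 and 11 have since replaced both the follow-up and the power. That stands, and it is why the point is minor.

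A second reply concerns two stronger conclusions that a reader might draw. One is that Appendix 1's own assumptions give 0.81 for the section 2.E design, so that the promised power is not delivered. The documents do not support this. The value 0.81 needs a hazard ratio of 0.70, even crossover and a constant hazard together. The appendix words the effect as a reduction in incidence, and the same model then gives about 0.84. End-of-year crossover gives 0.86 to 0.89. A front-loaded hazard is plausible too, since section 4.A describes patients beyond 90 days as past the period of highest risk.

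The other is that 0.84 depended on longer follow-up than the design offers. A plain fixed three-year comparison reproduces 0.84, and in every constant-hazard variant 2 to 5 years gives more power than a fixed three years, because mean follow-up is 3.5 years. The loss exists only against a genuine three-year minimum.

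Neither reply removes the contradiction. Section 2.E states a floor that its cited source does not reach, and the source assumes a follow-up that section 2.E does not provide.

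**Conclusion.** Wrong as written, and minor. Two contradictions are on the page and need no modelling: at least 85% against 0.84, and a two-year against a three-year minimum. Under Appendix 1's inputs with uniform accrual, the section 2.E design has power of about 0.80 to 0.84 with constant hazard and evenly spread crossover, and about 0.73 to 0.89 when crossover timing varies; a front-loaded hazard can exceed that. These values fall on both sides of 85%, so the claim is neither derivable from the appendix nor refuted by it. The result rests on assumptions that the appendix leaves open: crossover timing, crossover after year 3, hazard shape and the meaning of the 30%. It concerns the base protocol only; the revision's figure of about .73 for 1675 patients governs current accrual.

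**What to change.** Make section 2.E and Appendix 1 state the same minimum follow-up and the same power. Replace the claim of at least 85% with the Appendix 1 figure, recomputed for the actual follow-up (last patient two years). Beside it, declare when crossover is taken to occur, whether it continues after year 3, the hazard shape, and whether the 30% is a cut in three-year incidence or a hazard ratio. Do not write in 0.81, which is one variant among several. Add a note that revision item 11 supersedes this power for current accrual.

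The cost is one recalculation and a text correction, with no change to conduct or analysis. The restated figure may be somewhat less favourable.
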